AST, ALT, or Increased Bilirubin	2	Toxicity resolves to Grade \leq 1	Toxicity does not resolve within 12 weeks of last dose
	3-4	Permanently discontinue (see exception below) ²	Permanently discontinue
Type 1 diabetes mellitus (if new onset) or Hyperglycemia	T1DM or 3-4	Hold pembrolizumab for new onset Type 1 diabetes mellitus or Grade 3-4 hyperglycemia associated with evidence of beta cell failure	Resume pembrolizumab when patients are clinically and metabolically stable
Hypophysitis	2-3	Toxicity resolves to Grade \leq 1	Toxicity does not resolve within 12 weeks of last dose or inability to reduce corticosteroid to 10 mg or less of prednisone or equivalent per day within 12 weeks
	4	Permanently discontinue	Permanently discontinue
Hyperthyroidism	3	Toxicity resolves to Grade \leq 1	Toxicity does not resolve within 12 weeks of last dose or inability to reduce corticosteroid to 10 mg or less of prednisone or equivalent per day within 12 weeks.
	4	Permanently discontinue	Permanently discontinue
Infusion Reaction	3-4	Permanently discontinue	Permanently discontinue
Pneumonitis	2	Toxicity resolves to Grade \leq 1	Toxicity does not resolve within 12 weeks of last dose or inability to reduce

Toxicity	Hold Treatment For Grade	Timing for Restarting Treatment	Discontinue Subject
			corticosteroid to 10 mg or less of prednisone or equivalent per day within 12 weeks
	3-4	Permanently discontinue	Permanently discontinue
Renal Failure or Nephritis	2	Toxicity resolves to Grade \leq 1	Toxicity does not resolve within 12 weeks of last dose or inability to reduce corticosteroid to 10 mg or less of prednisone or equivalent per day within 12 weeks
	3-4	Permanently discontinue	
Rash³	3 or Severe ^{4,5}	Toxicity improves to Grade \leq 2	Toxicity does not improve within 12 weeks of last dose or inability to reduce corticosteroid to 10 mg or less of prednisone or equivalent within 12 weeks
All Other Drug-Related Toxicity,³	3 or Severe ⁴	Toxicity resolves to Grade \leq 1	Toxicity does not resolve within 12 weeks of last dose or inability to reduce corticosteroid to 10 mg or less of prednisone or equivalent per day within 12 weeks
	4	Permanently discontinue	Permanently discontinue

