
Note: Permanently discontinue for any severe³ or Grade 3 drug-related AE that recurs or any life-threatening event.
 
¹ For grade 2 diarrhea which is attributed to cetuximab and sub-optimally managed with anti-diarrheal agents, Pembrolizumab may be continued. Patients should be seen in clinical follow-up within 1 week with additional phone follow-up within 72 hours. If optimally managed with anti-diarrheal agents and it is not felt that the toxicity is clearly cetuximab related, Pembrolizumab should be held until toxicity resolves to Grade \leq 1.
 
² For patients with liver metastasis who begin treatment with Grade 2 AST or ALT, if AST or ALT increases by greater than or equal to 50% relative to baseline and lasts for at least 1 week then patients should be discontinued.
 
³ Patients with intolerable or persistent Grade 2 drug-related AE may hold study medication at physician discretion. Permanently discontinue study drug for persistent Grade 2 adverse reactions for which treatment with study drug has been held, that do not recover to Grade 0-1 within 12 weeks of the last dose.
 
⁴ For these purposes, a severe toxicity is a toxicity which does not otherwise meet the criteria for grade 3 or 4, but which the investigator deems as being substantial enough to merit the holding of therapy.
 
⁵ For an acneiform or maculopapular rash which is deemed to be clearly related to cetuximab, at the investigator's discretion, pembrolizumab may be administered even for grade 3 rash, as long as the rash is showing signs of improvement and cetuximab is held as per protocol.
			

Dosing interruptions are permitted in the case of medical / surgical events or logistical reasons not related to study therapy (e.g., elective surgery, unrelated medical events, patient vacation, and/or holidays). Participants should be placed back on study therapy within 3 weeks of the scheduled interruption, unless otherwise discussed with the Sponsor. The reason for interruption should be documented in the patient's study record.

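### For a Grade 2 rash held as Severe that eases but stays at Grade 2, the Rash row of Table 1 (Section 6.1.1) allows pembrolizumab to restart while footnote 3 on that row requires permanent discontinuation

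*Combined protocol and SAP*

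**What the plan says.** All the text at issue is in Table 1 of Section 6.1.1 and the footnotes beneath it.

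- **Rash row, hold column:** Grade 3 or Severe, with footnotes 4 and 5 attached to Severe.
- **Rash row, restart column:** "Toxicity improves to Grade" 2 or lower.
- **Rash row, discontinuation column:** "Toxicity does not improve within 12 weeks of last dose", or the corticosteroid cannot be brought down to the stated prednisone-equivalent dose in that time.
- **Footnote 3, attached to the row label Rash:** it opens with a discretionary hold, "Patients with intolerable or persistent Grade 2 drug-related AE may hold study medication at physician discretion". It continues: "Permanently discontinue study drug for persistent Grade 2 adverse reactions for which treatment with study drug has been held, that do not recover to". The recovery demanded is to Grade 0 or 1, and the limit is 12 weeks counted from the last dose.
- **Footnote 4:** "a severe toxicity is a toxicity which does not otherwise meet the criteria for grade 3 or 4, but which the investigator deems as being". The test it then gives is the investigator's view that a hold is warranted.
- **All Other Drug-Related Toxicity row, directly below:** it also holds for Grade 3 or Severe and carries footnotes 3 and 4, but its restart grade is 1 or lower.

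**The concern.** A restart criterion should describe a state that the patient is not in when the drug is held. For a rash held at Grade 3, a threshold of Grade 2 or lower does that. For a rash held as Severe it does not, because footnote 4 places such a rash below Grade 3 by definition. Footnote 3, on the same row, then sets a different recovery grade and attaches permanent discontinuation to missing it.

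Section 6.3.11 expects rash of Grade 2 or 3 from both study drugs, so this row is likely to be consulted. Up to three sites enroll (Section 4.2). A site working from the row and a site working from the footnote could treat the same rash differently: one gives more pembrolizumab, the other ends it. In a single-arm study that adds pembrolizumab to cetuximab and lists the adverse event profile among its primary objectives (Section 3.1), exposure to the added drug should not depend on which line of a table is read.

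**Working it through.** The plan states no figure on this point and no arithmetic applies. The check follows a rash held as Severe through the row and through footnote 3.

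**Step 1: grade at the hold.** Footnote 4 excludes Grades 3 and 4, so a Severe rash is Grade 1 or 2.

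**Step 2: outcomes side by side.** Assume throughout that the rash counts as drug-related and that the row's corticosteroid condition is met.

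| Rash held as Severe | Rash row | Footnote 3 | Same answer? |
|---|---|---|---|
| Grade 1 at the hold, does not worsen | Restart grade met | Recovery grade met | Yes |
| Grade 2, falls to Grade 1 within 12 weeks | Restart allowed | Recovered | Yes |
| Grade 2, eases, still Grade 2 at 12 weeks | It has improved and is Grade 2: restart allowed, discontinuation criterion not met | Not at Grade 0-1: permanent discontinuation | **No** |
| Grade 2, no change at all by 12 weeks | If improvement is required: discontinue. If only the grade counts: restart allowed | Permanent discontinuation | Only if improvement is required |

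The third line is a contradiction however the word *improves* is read. The fourth depends on that reading.

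**Step 3: comparison with the next row.** The All Other Drug-Related Toxicity row uses the same Severe trigger and the same two footnotes. Because it restarts at Grade 1 or lower, a held Grade 2 toxicity cannot resume until it reaches the grade that footnote 3 asks for. Row and footnote agree there, so the clash lies in the Rash row's restart grade.

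**Step 4: search for a resolving rule.**
- Footnote 5 lets pembrolizumab be given, at the investigator's discretion, when an acneiform or maculopapular rash is clearly due to cetuximab. It sets no restart grade for a rash held as Severe.
- Section 6.3.11 deals with Grade 2 and Grade 3-4 skin events and gives no restart grade and no rule for a Severe rash below Grade 3.
- Section 6.4.1 covers skin care and cetuximab holds, not pembrolizumab restart.

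None of these says whether the row or footnote 3 prevails.

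**The case against.** **The verb.** The restart column asks that the rash improve, and the discontinuation column turns on its not improving. A Grade 2 rash that has not changed has not improved. An investigator who has just judged it bad enough to hold would hardly restart the same day. This stands: the documents do not support saying flatly that restart is permitted at the moment of the hold, and for a wholly unchanged rash the row and footnote 3 can be read to agree. It does not help the rash that eases within Grade 2.

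**The hold ends at restart.** One can argue that once the row allows dosing to resume, there is no longer a held reaction for footnote 3 to act on. The outcome would then depend on whether the site restarts early or waits, since a site that waits reaches the 12-week limit. The footnote's own discretionary hold for an intolerable or persistent Grade 2 event also overlaps with a Severe hold at Grade 2: both rest on the investigator's judgement, and nothing tells the site which it has used.

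**Stronger readings that a reader might infer:**
- *A Grade 3 rash that settles at Grade 2 is caught as well.* Footnote 3 opens with reactions held at Grade 2. A rash held at Grade 3 that drops to Grade 2 most naturally follows the row. Extending the footnote to it strains the text.
- *The diabetes and hyperglycemia row clashes with the Note under the table.* The Note stops the drug for any "drug-related AE that recurs or any life-threatening event", while that row says "Resume pembrolizumab when patients are clinically and metabolically stable". Equating Grade 4 hyperglycemia with life-threatening would borrow a label from Table 3, which grades infusion reactions. Section 10.2.1 defines life-threatening by immediate risk of death, not by grade.
- *Section 1.2 yields a count of affected patients.* The rates there of rash at Grade 2 or worse, 29% and 62%, come from a study of skin care during anti-EGFR therapy. They do not give the rate of pembrolizumab holds.

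**Conclusion.** The conflict is real and narrow: a drug-related Grade 2 rash, held as Severe, that eases but does not fall below Grade 2 has two stated outcomes in one table. The conclusion assumes that footnote 3 applies to such a hold, which its marker on the Rash label supports.

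The number of patients cannot be derived, because the documents give no rate for pembrolizumab holds due to rash or for rash persisting at Grade 2. It is probably small: enrollment is capped at 42, and several conditions must coincide.

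The effect is on uniform pembrolizumab exposure and rash handling across sites. A reader might go on to infer damage to the endpoints, but the documents do not support that:
- **6-month PFS:** Section 6.1 has cetuximab continue as appropriate when pembrolizumab is held or discontinued. Section 12.3 counts a failure when a patient leaves study therapy before 6 months and receives off-protocol therapy, so stopping pembrolizumab is not in itself a failure.
- **Safety analysis:** Section 12.4.1 tabulates maximum grade by preferred term and plans no count of discontinuations for toxicity.
- **Phase Ib rule:** the dose-limiting toxicity definition in Section 12.5 excludes rash below Grade 4, so a Severe rash does not enter it.

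**What to change.** Reconcile the Rash row of Table 1 in Section 6.1.1 with footnotes 3 and 4, so that a held rash at Grade 2 leads to one outcome whichever line a site reads. The text should also make clear which provision governs if row and footnote continue to differ. The threshold, and how the table is laid out to express it, are for the sponsor to decide.

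The cost is a wording change to one table and its footnotes in a protocol amendment, with no added visits, assessments or patients.

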6.1.2 Cetuximab

Dose Selection

Cetuximab will be administered as per the package insert. The initial loading dose (400 mg/m²) will be administered over 120 minutes. Subsequent doses will be delivered over 60 minutes

provided there are no significant infusion reactions. The package insert contains specific instructions for the preparation of the cetuximab infusion fluid and administration of infusion solution. As appropriate, dose modifications are to be pursued as per **Table 1**.

Table 1.

Dose Level (DL)	Pembrolizumab (mg)	Cetuximab** (mg)
Regimen I: Pembrolizumab + Cetuximab		
-2	200 mg every 3 weeks	150 mg/m ² weekly
-1	200 mg every 3 weeks	200 mg/m ² weekly
*1	200 mg every 3 weeks	250 mg/m ² weekly

**Cetuximab is administered with a loading dose of 400 mg/m² to be administered on cycle 1 day 1, at all dose levels.

Timing of Dose Administration

Trial treatment will be administered on Days 1, 8 and 15 of each cycle after all procedures/assessments have been completed (as detailed in **Table 4** Schedule of Procedures and Observations). Of note, the results of laboratory tests which are send-out tests (including TFTs) are not necessary prior to treatment. Trial treatment may be administered up to 3 days before or after the scheduled Day 1 of each cycle due to administrative reasons.

All trial treatments will be administered on an outpatient basis.

Cetuximab Dose Modification and Treatment Delay Guidelines

Table 2 Dose Modification Guidelines for Drug-Related Adverse Events: Cetuximab

Worst toxicity observed (NCI CTCAE version 4.0)	Subsequent administration
Skin Toxicity (e.g. Acneiform rash, deemed attributable to cetuximab)	
Grade 1 or 2	
 Continue at same dose level
Grade 3 or 4: 1st occurrence ¹	
 Delay infusion one to two weeks Once symptoms improve, continue dosing at same dose level. If there is no improvement in symptoms for ≥ 4 weeks, discontinue cetuximab.
Grade 3 or 4: 2nd occurrence	
 Delay infusion one to two weeks Once symptoms improve, continue dosing and reduce by one dose level If there is no improvement in symptoms for ≥ 4 weeks, discontinue cetuximab.

Worst toxicity observed (NCI CTCAE version 4.0)	Subsequent administration
Grade 3 or 4: 3rd occurrence	
 • Delay infusion one to two weeks • Once symptoms improve, continue dosing and reduce by one further dose level • If there is no improvement in symptoms for ≥ 4 weeks, discontinue cetuximab.
Grade 3 or 4: 4th occurrence	
 • Discontinue cetuximab
Diarrhea	
Grade 1	
 • Continue at same dose level
Grade 2 ²	
 • If anti-motility agents not maximized, maximize supportive care.¹ • If anti-motility agents maximized, hold cetuximab. When symptoms improve to \leq grade 1, resume with dose reduced by one dose level
Grade 3 or 4	
 • Hold cetuximab until adequate resolution • If symptoms improve to grade 1, resume with dose reduced by one dose level • If symptoms do not improve within 2 weeks, permanently discontinue
Respiratory toxicity	
Acute onset or worsening pulmonary symptoms	
 • Interrupt cetuximab dosing
Confirmed ILD	
 • Permanently discontinue cetuximab
Infusion reaction	
 • Reduce the infusion rate by 50% for NCI CTC Grade 1 or 2 and non-serious NCI CTC Grade 3 infusion reactions. Immediately and permanently discontinue cetuximab for serious infusion reactions, requiring medical intervention and/or hospitalization.

18. For patients who find the rash to be intolerable, the dose may be reduced at the investigator's discretion.

19. Additionally refer to 6.3.2. Patients who are receiving additional supportive care measures require close follow-up, minimally within 72 hours by phone and 7 days in clinic.

6.2 General Concomitant Medications

Medications or vaccinations specifically prohibited in the exclusion criteria are not allowed during the ongoing trial. If there is a clinical indication for one of these or other medications or vaccinations specifically prohibited during the trial, discontinuation from trial therapy or vaccination may be required. The investigator should discuss any questions regarding this with the Sponsor/Merck Clinical team. The final decision on any supportive therapy or vaccination rests with the investigator and/or the participant's primary physician.

Participants may be pretreated for nausea and vomiting with appropriate anti-emetics.

6.2.1 Acceptable Concomitant Medications

All treatments that the investigator considers necessary for a participant's welfare may be administered at the discretion of the investigator in keeping with the community standards of

medical care. All concomitant medication will be recorded on the case report form (CRF) including all prescription, over-the-counter (OTC), herbal supplements, and IV medications and fluids. If changes occur during the trial period, documentation of drug dosage, frequency, route, and date may also be included on the CRF.

All concomitant medications received within 1 week prior to the first dose of trial treatment and 30 days after the last dose of trial treatment or a new treatment is started, whichever comes first, will be recorded". Concomitant medications administered after 30 days after the last dose of trial treatment will be recorded for SAEs and ECIs as defined in **Section 10**).

Participants may be pretreated for nausea and vomiting with appropriate anti-emetics.

6.2.2 Prohibited Concomitant Medications

Participants are prohibited from receiving the following therapies during the Screening and Treatment Phase (including retreatment for post-complete response relapse) of this trial:

- Antineoplastic systemic chemotherapy or biological therapy
- Immunotherapy not specified in this protocol
- Chemotherapy not specified in this protocol
- Investigational agents other than pembrolizumab
- Radiation therapy
 - Note: Radiation therapy to a symptomatic solitary lesion or to the brain may be allowed at the investigator's discretion.
- Live vaccines within 30 days prior to the first dose of trial treatment and while participating in the trial. Examples of live vaccines include, but are not limited to, the following: measles, mumps, rubella, varicella/zoster, yellow fever, rabies, BCG, and shingles.
- Systemic glucocorticoids for any purpose other than to modulate symptoms from an event of clinical interest of suspected immunologic etiology (and as described for grade 3 cetuximab AEs). The use of physiologic doses of corticosteroids may be approved after consultation with the Sponsor. NOTE: Brief courses of steroids to prevent allergic reactions (IV contrast dye) or for similar purposes are permitted, but should first be reviewed with the sponsor.

Subjects who, in the assessment by the investigator, require the use of any of the aforementioned treatments for clinical management should be removed from the trial. Subjects may receive other medications that the investigator deems to be medically necessary.

The Exclusion Criteria (**Section 5.2**) describe other medications which are prohibited in this trial.

6.3 Supportive Care Guidelines for Pembrolizumab

Participants should receive appropriate supportive care measures as deemed necessary by the treating investigator. Suggested supportive care measures for the management of adverse events with potential immunologic etiology are outlined below and in greater detail in the

ECI Guidance Document. Where appropriate, these guidelines include the use of oral or intravenous corticosteroids as well as additional anti-inflammatory agents if symptoms do not improve with administration of corticosteroids. Note that several courses of steroid tapering may be necessary as symptoms may worsen when the steroid dose is decreased. For each disorder, attempts should be made to rule out other causes such as metastatic disease or bacterial or viral infection, which might require additional supportive care. The treatment guidelines are intended to be applied when the investigator determines the events to be related to pembrolizumab.

Note: If after the evaluation the event is determined not to be related to the study drug, the investigator is instructed to follow the ECI reporting guidance but does not need to follow the treatment guidance (as outlined in the ECI Guidance Document). Refer to **Section 6.1.1** for dose modification.

It may be necessary to perform conditional procedures such as bronchoscopy, endoscopy, or skin photography as part of evaluation of the event. Suggested conditional procedures, as appropriate, can be found in the ECI Guidance Document.

Note: All adverse events, regardless of grade, that are considered Events of Clinical Interest should be reported regardless of etiology.

6.3.1 Pneumonitis

- For **Grade 2 events**, treat with systemic corticosteroids. When symptoms improve to Grade 1 or less, steroid taper should be started and continued over no less than 4 weeks.
- For **Grade 3-4 events**, immediately treat with intravenous steroids. Administer additional anti-inflammatory measures, as needed.
- Add prophylactic antibiotics for opportunistic infections in the case of prolonged steroid administration.

6.3.2 Diarrhea/Colitis

Participants should be carefully monitored for signs and symptoms of enterocolitis (such as diarrhea, abdominal pain, blood or mucus in stool, with or without fever) and of bowel perforation (such as peritoneal signs and ileus). Diarrhea from Pembrolizumab most commonly presents at 6 weeks or later during therapy. If cetuximab is suspected as the etiology, particularly if early onset within the first 6 weeks, anti-motility agents and close f/u along with appropriate cetuximab management should be instituted.

- All participants who experience diarrhea/colitis should be advised to drink liberal quantities of clear fluids. If sufficient oral fluid intake is not feasible, fluid and electrolytes should be substituted via IV infusion. Anti-motility agents (e.g. loperamide, diphenoxylate/atropine) may be utilized initially.
- For Grade 2 diarrhea/colitis, first initiate above supportive measures and initiate or intensify anti-motility agents. Close clinical f/u is necessary (i.e. follow-up via phone within 72 hours and in clinic within 7 days). If cetuximab is held and symptoms are still not improving promptly, or there is suspicion for Pembrolizumab toxicity, consider GI

consultation and endoscopy to rule out or confirm colitis. If suspicion for pembrolizumab related colitis is high and/or endoscopy cannot be performed promptly, administer oral corticosteroids. For Grade 3 or 4 diarrhea/ colitis that persist for > 1 week, treat with intravenous steroids followed by high dose oral steroids.

- When symptoms improve to Grade 1 or less, steroid taper should be started and continued over no less than 4 weeks.

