1.5 Risks and/or Benefits

The most common adverse effects of cetuximab include rash, hypomagnesemia, infusion reactions and diarrhea. Grade III/IV dermatologic reactions occur in up to 5% of patients with infusion reactions in up to 4.5%.

Pembrolizumab has been well tolerated thus far, with the most common adverse effects (reported in $\geq 20\%$ of patients) being fatigue, cough, nausea, pruritus, rash, decreased appetite, constipation, arthralgia, and diarrhea.

Currently, there is no published data on the combination of EGFR antibodies and anti PD-1 therapy for treatment of metastatic colorectal cancer. At least two studies have combined anti-EGFR TKIs and anti-PD-1 or anti-PD-L1 antibodies. Nivolumab (anti-PD-1) and erlotinib (EGFR TKI) have been combined in chemotherapy-naive advanced NSCLC (21). In the 21 patients reported to date, this was well tolerated. While there was a 71% incidence of rash, there was no grade 3/4 rash. A 10% incidence of grade 3/4 diarrhea as well as grade 3/4 transaminitis was observed. Though all but 1 patient had previous erlotinib resistance, 15% of patients were seen to have responses with a 24 week PFS of 51%. Similarly, safety and tolerability data have recently been reported on a phase I study of MEDI-4736 (anti-PD-L1) and gefitinib (EGFR TKI)(22). Generally, the treatment was well tolerated. Unexpected AEs did not emerge. There was an increase in grade 3 transaminitis, though only 2/15 (15%) of patients in the expansion cohort ultimately discontinued therapy due to AEs. Thus, there is reason to believe anti-EGFR inhibition can be safely combined with PD-1 inhibition and may have clinical efficacy in advanced cancer.

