6 TREATMENT PLAN

6.1 Dosing and Administration

The treatment regimen to be used in this trial is outlined below:

Cetuximab 400 mg/m² loading dose on day 1 cycle 1, followed by 250 mg/m² intravenously weekly. Pembrolizumab 200 mg fixed dose intravenously every 3 weeks.

Reported adverse events (AEs) and potential risks are described in **Section 1.5**. Appropriate dose modifications are described in **Section 6.1**

A cycle is defined as 3 weeks of treatment, with cetuximab administered weekly and pembrolizumab administered every 3 weeks, on day 1 of each cycle. Absent relevant limiting toxicities, pembrolizumab may be administered even if cetuximab is to be held on day 1 for cetuximab related AEs. Likewise, in the instance of pembrolizumab related AEs which require dose holding or discontinuation, cetuximab administration should continue as appropriate. Cetuximab will be administered prior to pembrolizumab on day 1, due to concern for infusion reactions. Pembrolizumab may be administered on Day 2 of any cycle in the event of a Cetuximab related infusion reaction; or any other adverse event at the discretion of the PI.

If cetuximab is held for greater than 2 weeks for reasons other than cetuximab related adverse events, the 400 mg/m² loading dose may be readministered upon resumption, at the discretion of the investigator.

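### In Section 6.3.2 the steroid triggers run against severity: Grade 2 diarrhea/colitis has no minimum duration, while the Grade 3-4 instruction covers only events lasting more than 1 week

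*Combined protocol and SAP*

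**What the plan says.** Section 6.3.2 covers diarrhea and colitis under the supportive care guidelines for pembrolizumab. Fluids and anti-motility agents apply to all affected participants. One bullet then deals with grades 2 to 4.

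- **Grade 2.** Supportive care comes first: "For Grade 2 diarrhea/colitis, first initiate above supportive measures and initiate or intensify anti-motility agents". Contact times are given: "follow-up via phone within 72 hours and in clinic within 7 days". The steroid trigger is: "If suspicion for pembrolizumab related colitis is high and/or endoscopy cannot be performed promptly, administer oral corticosteroids".
- **Grade 3-4.** The only steroid instruction is: "For Grade 3 or 4 diarrhea/ colitis that persist for > 1 week, treat with intravenous steroids followed by high dose oral steroids".

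The parent Section 6.3 says its treatment guidance is meant for events the investigator judges to be related to pembrolizumab.

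Two other places govern cetuximab during the same event. In Section 6.1.2, the Table 2 diarrhea row holds cetuximab at Grade 3 or 4 and adds: "If symptoms do not improve within 2 weeks, permanently discontinue". Section 6.1 says that when a pembrolizumab-related event requires a hold or discontinuation, "cetuximab administration should continue as appropriate".

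**The concern.** A site reading the bullet as written finds a suspicion-based trigger with no day count for the milder event, and a duration condition for the more severe one. It finds nothing on steroids for a Grade 3-4 event in its first week, and no contact interval. The protocol gives no reason for the difference.

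Diarrhea is listed among the common effects of both drugs in Section 1.5, so uncertain attribution is foreseeable. Table 1 footnote 1 helps sites with attribution for Grade 2 diarrhea only. At Grade 3-4, where both dose-modification tables contain permanent discontinuation rules, there is no equivalent. The stake is patient safety and consistent handling of a shared toxicity across three sites, in a trial where the adverse event profile is a primary objective.

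**Working it through.** The plan states no figure on this point. The check is a comparison of text, followed by day arithmetic for the secondary point.

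**1. The two sentences side by side (Section 6.3.2)**

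| | Grade 2 | Grade 3-4 |
|---|---|---|
| Steroid trigger | High suspicion of pembrolizumab colitis and/or no prompt endoscopy | Persistence beyond 1 week |
| Minimum duration | None stated; supportive measures come first | More than 7 days |
| Steroid instruction in week 1 | Yes, if the trigger is met | None |
| Follow-up interval | 72 hours by phone, 7 days in clinic | None |

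Holding suspicion constant and high, the Grade 2 trigger can be met as soon as supportive measures have been started. The Grade 3-4 condition cannot be met before day 8. The order is inverted.

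**2. Could attribution explain it?** The Grade 3-4 sentence carries no cetuximab qualifier, and Section 6.3 already confines its treatment guidance to events judged pembrolizumab-related. Cetuximab attribution therefore does not account for the wait.

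**3. Is it the pattern elsewhere in 6.3?** For Grade 3-4 pneumonitis, Section 6.3.1 says "immediately treat with intravenous steroids". The Grade 3-4 steroid rules for hypophysitis (6.3.4), hyperthyroidism (6.3.5), hematologic (6.3.6), hepatic (6.3.7), neurologic (6.3.8), ocular (6.3.9), renal (6.3.10) and other events (6.3.12) carry no persistence condition. Skin (6.3.11) has none in its main rule. It does allow steroids to be deferred for a tolerable maculopapular rash of Grade 3 or higher strongly felt to be due to cetuximab, with weekly follow-up and discussion with the PI. That deferral states its attribution condition; the one in 6.3.2 does not.

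**4. Overlap with the 2-week cetuximab limit**

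Inputs: the persistence condition is more than 7 days (6.3.2), and the cetuximab limit is 14 days without improvement (Table 2). Table 2 does not say when its 2 weeks start. Let that clock start *d* days after onset (an assumption).

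Days left when the persistence condition is first met: fewer than (d + 14) - 7 = d + 7.

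- d = 0 (both run from onset): fewer than 7 of the 14 days remain.
- d = 7 (clock starts at a weekly dose held 7 days after onset): fewer than 14 remain.

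This matters only if both rules apply to the same event. The Table 2 skin row is limited to toxicity deemed attributable to cetuximab, whereas the diarrhea row has no such phrase. A Table 2 footnote on Grade 2 diarrhea also sends the reader to 6.3.2. The table title, however, restricts it to drug-related events of cetuximab, and Section 6.1 has cetuximab continue for pembrolizumab-related events. The overlap therefore arises when attribution is to both drugs or is not yet settled.

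**The case against.** The strongest reply is that 6.3.2 does not prohibit anything. Section 6.3 calls its measures suggested and leaves them to the treating investigator. It refers to an ECI Guidance Document for more detail, which is not among the documents reviewed. Section 6.2.2 permits systemic glucocorticoids for an event of clinical interest of suspected immunologic origin, and Table 10 includes diarrhea and colitis from Grade 2 upward. A reader might infer that the protocol requires a week without steroids at Grade 3-4; the documents do not support that. This part of the reply stands, and it makes the point one of inconsistent wording. It does not explain why the worse grade alone carries a duration condition.

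The reply also holds that Grade 2 steroids are not unconditional, because supportive measures come first and suspicion or endoscopy access decides. That is correct, but it is a sequence and not a number of days.

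Third, scope largely separates the two cetuximab rules: Table 2 is for cetuximab-related events, Section 6.3 for pembrolizumab-related ones, and Section 6.1 fits that split. A reader might infer an outright contradiction between 6.3.2 and Table 2; there is none when attribution is clear. What remains is the mixed or unsettled case, for which the diarrhea row gives no instruction.

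**Conclusion.** The inconsistency within 6.3.2 holds on the text alone and needs no assumption beyond equal suspicion at both grades. The overlap with Table 2 is secondary. It rests on mixed or unsettled attribution and on when the 2 weeks start; if both clocks run from onset, fewer than 7 of 14 days remain.

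Three stronger readings are tempting and are not supported:

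- **That the wait exhausts the cetuximab limit.** It takes somewhat more than half of the 14 days at most when d = 0, and the Table 2 test is failure to improve, not failure to resolve.
- **That about 4 patients would be affected.** Section 1.5 reports "A 10% incidence of grade 3/4 diarrhea as well as grade 3/4 transaminitis was observed", and 42 x 0.10 = 4.2. That rate is for all Grade 3/4 diarrhea, without duration or attribution, in 21 lung cancer patients on nivolumab plus erlotinib. The sentence in 6.3.2 concerns persistent, pembrolizumab-related events, whose frequency the documents do not give.
- **That the rule drives events to Grade 4 or inflates the maximum-grade table of Section 12.4.1.** Nothing in the documents shows either.

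The point should be addressed because the bullet is a stated instruction on a foreseeable serious toxicity. It has no bearing on sample size, error rates or the primary efficacy tests.

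**What to change.** 1. In Section 6.3.2, the sponsor's clinicians should reconcile the Grade 2 and Grade 3-4 sentences with each other, or state why the triggers differ. The text should make clear what instruction and what follow-up interval govern the first week of a Grade 3-4 event.
2. In the Table 2 diarrhea row, state whether it applies to diarrhea attributed to pembrolizumab or to both drugs, consistently with Section 6.1. Stating the day from which the 2 weeks are counted would remove the remaining ambiguity.

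The content of the rule is for the clinicians, and none is proposed here. The cost is a few sentences in 6.3.2 and a phrase in one table row, carried in a protocol revision with the IRB approval that Section 16.1 requires. No analysis changes.
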